Inclusion criteria: (1) aged 18 years or above; (2) patients with one or more peripheral lung nodules suspected to be lung cancer or poorly absorbing lesions on conventional anti-infective therapy; (3) patients with nodule diameters \leq 30 mm (diameters mentioned in the text are the average of the maximum and minimum diameters; (4) the nodules were pure ground glass nodules, partially solid nodules, or solid nodules; (5) the nodule is surrounded by lung parenchyma and is not visible in the bronchial lumen above the segment.

Exclusion criteria: (1) preoperative judgment that it is difficult for the patient to benefit from bronchoscopic biopsy (e.g., high risk of bleeding due to perivascular encasement of the lesion, difficulty in reaching the airway adjacent to the lesion due to previous lung surgery, etc.); (2) those with incomplete clinical data; (3) those with missing visits after biopsy.

Interventions

After stratification according to the size of the lesion and the proportion of solid components in the lesion (\geq 50%, <50%), the eligible subjects were randomized into the new navigation system group (experimental group) and the old navigation system group (control group) in a 1:1 ratio. All included subjects underwent transnavigation-guided bronchoscopic lung biopsy at the respiratory endoscopy center. For pre-biopsy navigation path planning, the small airway reconstruction system-pro (SARS-pro) (self-developed by our team) was used in the experimental group and the conventional VBN system (LungPro; Bronchus Corporation) in the control group. The SARS-pro navigation system is an augmented reality optical navigation system based on VBN, which upgrades the small airway tree reconstruction navigation system through deep learning and multiple trainings.

Outcomes

The primary outcome was the diagnostic positive yield of the different navigation systems for PPL. The second outcome was the adverse events (hemoptysis, pneumothorax, and mediastinal emphysema) of the subjects.

Ethical approval and informed consent statement

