The trial was approved by the Ethics Committee of the Sir Run Run Shaw Hospital, Zhejiang University School of Medicine (approval number: 2024-1000) (See the attachment "Ethics Approval Document"). For statistical analysis, subject identities were expressed as codes, which did not involve disclosure of subjects' privacy and personal information, and the study did not involve commercial interests, so informed consent was waived by the Ethics Committee (See the attachment "Informed consent form").

Statistical analysis plan

Official Title of the study: Research on New Intelligent Diagnosis and Treatment Technologies for Early Lung Cancer Based on Multimodal Imaging Bronchoscopy Navigation

Date of the document: May 20, 2024

Research on New Intelligent Diagnosis and Treatment Technologies for Early Lung Cancer Based on Multimodal Imaging Bronchoscopy Navigation

Statistical analysis

For sample size calculation, a study reported a deep learning-based airway segmentation algorithm based on 40 CT images. Based on the benefit of a larger sample size in deep learning, the sample size in this study was set to 100. For subject characteristics, the quantitative data were tested for normality using the skewness and kurtosis methods, and the homogeneity of variance was tested using the Levene test. Normal distribution measurement data were described as mean and standard deviation [Mean (±SD)], and t test or t' test was utilized for comparison between groups. Nonnormal data were summarized as median and interquartile range [M (Q_1 , Q_3)], and group comparisons were made using the Wilcoxon rank sum test. Count data were reported as the number of cases and composition ratio [n (%)], and the chi-square test or the Fisher exact test was utilized for comparison between groups. Data cleaning was accomplished using Python 3.9.12 (Python Software Foundation, Delaware, USA), and the difference comparison was completed by R version 4.3.3 (R Foundation for Statistical Computing, Vienna, Austria). Statistical significance was set to P<0.05.

Data management and confidentiality

(1) The data is stored in the hospital's server with strict security protection and is not accessible to external networks; (2) All information related to the identity of the CT's patients is kept confidential, and the relevant information is not disclosed to the public outside of the scope permitted by relevant laws and/or regulations.

Ethics Committee Approval (Original Chinese version)

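### Exclusion for missed visits after biopsy removes subjects already randomised and biopsied, and can bias both the yield and the adverse-event comparisons

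*Combined protocol and SAP*

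**What the plan says.** The protocol section on inclusion and exclusion criteria has three exclusions. The third is "those with missing visits after biopsy". The second, "2) those with incomplete clinical data", has no time point.

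The Interventions section gives the order of events. After stratification, "the eligible subjects were randomized into the new navigation system group (experimental group") or the control group, 1:1. The assigned system is used to plan the path before biopsy, and then "All included subjects underwent transnavigation-guided bronchoscopic lung biopsy at the respiratory endoscopy center".

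Under Outcomes: "The primary outcome was the diagnostic positive yield of the different navigation systems for PPL", and "The second outcome was the adverse events (hemoptysis, pneumothorax, and mediastinal emphysema) of the subjects". Neither the denominator of the yield nor the observation window for adverse events is given.

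In the SAP's Statistical analysis section, "the sample size in this study was set to 100", and for count data "the chi-square test or the Fisher exact test was utilized for comparison between groups". The section names no analysis set, missing-data rule, allowance for loss or sensitivity analysis.

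**The concern.** An eligibility criterion has to be assessable before allocation. Criterion (3) is not: whether a visit after biopsy was missed is unknown until the subject has been randomised, planned with the assigned system and biopsied. In practice it removes randomised subjects from the analysis. Criterion (2) is acceptable if it means data required before randomisation, and has the same fault if it covers data collected later.

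Both outcomes are affected. If attendance is related to the biopsy result and the relation differs between arms, the subjects who remain are no longer comparable and a false difference in yield can appear. Losing non-diagnostic subjects raises an arm's apparent yield. Losing diagnosed subjects, for example those who go elsewhere for treatment, lowers it. A subject who has an adverse event at the procedure and then misses visits disappears from the safety comparison.

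The documents do not say how many visits there are, when they fall, or whether they help settle the diagnosis. The direction of any bias is therefore unknown, and the plan has nothing that would limit or reveal it.

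**Working it through.** **Timing.** The order is: eligibility, randomisation, path planning with the assigned system, biopsy, later visits. Criterion (3) refers to the last step. The phrase about eligible subjects being randomised cannot rescue it, because no subject can meet or fail this criterion at randomisation.

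**Inputs.**
- From the documents: total 100, 1:1 allocation, chi-square or Fisher test, significance at 0.05, and a background yield of 80% for navigation bronchoscopy.
- Assumed: 50 per arm, a two-sided test, 80% as the true yield in both arms, and all loss rates. The total of 100 rests on no effect size or loss rate, so there is no figure of the plan's own to reproduce.

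**Apparent yield after exclusion.** With true yield p, and fractions d of diagnosed and q of non-diagnostic subjects lost:

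apparent yield = p(1 − d) / [p(1 − d) + (1 − p)(1 − q)]

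- q = 0.40: 0.80 / (0.80 + 0.20 × 0.60) = 0.80 / 0.92 = 87.0%
- q = 0.10: 0.80 / (0.80 + 0.20 × 0.90) = 0.80 / 0.98 = 81.6%
- d = 0.40: 0.48 / (0.48 + 0.20) = 70.6%
- d = 0.10: 0.72 / (0.72 + 0.20) = 78.3%

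**Type I error.** In each arm the 50 subjects fall into retained diagnosed, retained non-diagnostic and lost (a trinomial). The rejection rate for the chi-square test was found by exact enumeration, and for Fisher's test by simulation with 40,000 replicates per scenario. The SAP does not say whether chi-square is continuity-corrected, so both are shown.

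| Loss (arm 1 vs arm 2), true yield 80% in both | Apparent yields | Uncorrected | Corrected | Fisher |
|---|---|---|---|---|
| None | 80% vs 80% | 5.2% | 2.8% | 2.8% |
| Unrelated to result, 20% vs 5% of all | 80% vs 80% | 5.1% | 2.5% | 3.7% |
| Non-diagnostic, 30% vs 30% | 85.1% vs 85.1% | 5.1% | 2.4% | 3.1% |
| Non-diagnostic, 20% vs 10% | 83.3% vs 81.6% | 5.7% | 2.9% | 3.7% |
| Non-diagnostic, 40% vs 10% | 87.0% vs 81.6% | 10.9% | 6.0% | 7.7% |
| Diagnosed, 40% vs 10% | 70.6% vs 78.3% | 12.8% | 8.0% | 10.1% |

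**Power under equal loss.** Take true yields of 95% and 80% and lose 30% of non-diagnostic subjects in each arm. The apparent yields are 0.95 / (0.95 + 0.05 × 0.70) = 96.4% and 0.80 / (0.80 + 0.20 × 0.70) = 85.1%, so a 15-point difference shrinks to 11.3 points. Power falls from 66% to 52% (uncorrected), 51% to 34% (corrected) and 51% to 43% (Fisher).

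**Worked case.** True result 40/50 versus 40/50, with 4 and 1 non-diagnostic subjects missing visits.
- Exclusion as written: 40/46 − 40/49 = 87.0% − 81.6% = +5.3 points.
- All randomised, unresolved counted as not diagnosed: 40/50 − 40/50 = 0.
- Best case for arm 1: 44/50 − 40/50 = +8.0 points.
- Worst case for arm 1: 40/50 − 41/50 = −2.0 points.

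**Adverse events.** At the 2% pneumothorax rate in the Background section, 50 × 0.02 = 1 event per arm is expected. If that one subject is excluded, the arm's observed rate becomes 0%.

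**The case against.** The strongest objection is to the remedy. Counting unresolved subjects as not diagnosed is itself an assumption and can do harm. Suppose the diagnosis needs the visits, and 20% versus 5% of subjects are lost for reasons unrelated to the result. If every lost subject counts as not diagnosed, an equal 80% becomes 0.80 × 0.80 = 64% versus 0.80 × 0.95 = 76%. The type I error is then 25.7% uncorrected and 19.6% corrected, against 5.1% and 2.5% under exclusion. The arithmetic is right, but the case requires every lost subject to be unresolved. The proposed rule keeps a subject with a diagnostic biopsy as diagnosed whatever visits are missed, and the complete-case and best/worst-case analyses would show the dependence. What stands is that the plan should first say what establishes a diagnosis. If the specimen alone settles it, missed visits give no reason to remove anyone from the yield analysis.

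Three smaller points also have substance:
- The loss rates are illustrative, and several scenarios show almost no effect. Losing 40% versus 10% of diagnosed subjects (about 16 versus 4 of 50) is a heavy imbalance, whereas 40% versus 10% of non-diagnostic subjects is only about 4 versus 1.
- If 100 means subjects analysed, with excluded subjects replaced, the power loss is overstated. The bias remains.
- The document is dated May 2024 and recruitment is given as August 2023 to December 2024, so subjects may already have been removed. That adds data recovery to the cost.

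None of these disputes that criterion (3) operates after randomisation.

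**Conclusion.** The concern holds: criterion (3) is wrong as written. This follows from the order of events and does not depend on the illustrative figures.

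The size of the bias is unknown. At 50 per arm and a true 80% in both, it ranges from negligible (unrelated, equal or mildly unequal loss) to roughly double or more the usual error under marked, result-related imbalance, and it can favour either arm. Equal loss of non-diagnostic subjects creates no false difference under equal true yields, but it overstates both yields, shrinks a true difference and lowers power. A retained exclusion of this kind undermines the randomised comparison for both outcomes, and it is easy to remove, so it should be corrected before the analysis.

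**What to change.** 1. Delete exclusion criterion (3). Restrict criterion (2) to named data items required before randomisation.
2. Define diagnostic yield, and say whether the biopsy specimen alone settles it or later visits contribute.
3. In the SAP, analyse every randomised subject in the assigned group. For the primary outcome, count a subject without an established diagnosis (no biopsy, no usable specimen, or unresolved because data or visits are missing) as not diagnosed. A subject with a diagnostic biopsy stays diagnosed even if later visits are missed.
4. Keep every biopsied subject in the adverse-event analysis. State the observation window and how subjects with incomplete follow-up are counted.
5. Add complete-case and best/worst-case sensitivity analyses for the yield.
6. Report losses by arm, with reasons.

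The cost is protocol and SAP wording and two simple sensitivity analyses. On the documents' own dates enrolment had begun, so the allocation, biopsy result and adverse-event data of anyone already removed would have to be recovered, and the change recorded as made during the trial. Both reported yields may be slightly lower.

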Even so, navigational bronchoscopy techniques have limitations in the management of peripheral lung nodules. Navigation bronchoscopy has limitations in the diagnosis and treatment of peripheral lung nodules. Data show that the overall diagnostic rate of navigation bronchoscopy for biopsy of peripheral lung nodules is 80%, which is lower than that of traditional CT-guided percutaneous lung puncture, especially for near-pleural foci and foci with a diameter of less than 1 cm. There are three reasons for this. First, the current mainstream navigation system based on CT images does not have enough ability to recognize airways smaller than 3 mm, and intraoperative blindness exists in some of the small airway areas, resulting in failure or inaccuracy of preoperative bronchoscopic path planning in some areas. Second, the current mainstream bronchoscopy equipment apex outer diameter is generally around 4-5mm, which cannot enter the finer distal small airways, and it is difficult to reach some peripheral lesions close to the subpleural area, which makes it difficult to increase the biopsy positivity rate of this part of the lesion. Third, the small airways around the lesions are in a collapsed state due to various reasons such as sputum stasis, insufficient inspiration or breath holding during the acquisition of CT images, so it is difficult for preoperative CT to truly reflect the situation of the patient's airway, which ultimately results in the difference between the real-time observation of the distribution of the airway and the pathway of the preoperative planning, and makes it impossible to realize the accurate guidance in the intraoperative period.

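### The primary outcome has no stated denominator or analysis set, so randomised subjects with no usable path or no biopsy could be dropped at the step the trial is testing

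*Combined protocol and SAP*

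**What the plan says.** The Background gives three reasons why navigation bronchoscopy does not diagnose more nodules. The first is poor recognition of airways under 3 mm, "resulting in failure or inaccuracy of preoperative bronchoscopic path planning in some areas". It later lists the control system, LungPro, among the systems that reconstruct these airways poorly, and presents the new algorithm as the answer.

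Interventions places the difference between the arms at this step: "For pre-biopsy navigation path planning, the small airway reconstruction system-pro (SARS-pro) (self-developed by our team) was used in the experimental group", with LungPro used in the control group. The same paragraph says that eligible subjects were randomised 1:1, and then: "All included subjects underwent transnavigation-guided bronchoscopic lung biopsy at the respiratory endoscopy center".

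On the outcome, the protocol says only: "The primary outcome was the diagnostic positive yield of the different navigation systems for PPL". The SAP gives a chi-square or Fisher exact test for count data. Neither part states a numerator, a denominator, an analysis set, or how to count a subject with no path, a lesion not reached or no biopsy.

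The exclusion criteria include (1) a "preoperative judgment that it is difficult for the patient to benefit from bronchoscopic biopsy", with vascular encasement and previous lung surgery among the examples; (2) "those with incomplete clinical data"; and (3) "those with missing visits after biopsy".

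**The concern.** Planning with the assigned system comes after randomisation and before biopsy. A planning failure is therefore a result of the assigned system, and it belongs in the comparison of systems. The plan does not say where it goes.

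The text leaves room for such a subject to disappear. Included is not defined as randomised. Criterion (3) can be applied only after the procedure, so the protocol already allows removal after randomisation. Criterion (2) could take out a subject who has no biopsy result. An analyst following the text could end with yield among biopsied subjects and believe the plan had been kept.

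At stake is whether the trial estimates the effect of the navigation system or only compares yield in two groups selected by that system. If the old system loses more subjects at planning, leaving them out hides the benefit under test. If the new system loses more, leaving them out flatters it.

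**Working it through.** **Inputs**

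- Yield once biopsied, q: 80% in both arms. The figure is borrowed from the Background, which says "the overall diagnostic rate of navigation bronchoscopy for biopsy of peripheral lung nodules is 80"%. It is an overall rate and is not stated as a design assumption for the control arm.
- Planning failure, f_C in control and f_E in the new arm: **assumed**, since the documents give no frequency. Range used: f_C of 5% to 15%, with f_E = 0.
- Sample size: 100, taken here as the total, so 50 per arm (also an assumption). The SAP derives it from a segmentation study on 40 CT images, with no rates, effect or power, so it cannot be reproduced and contains no allowance for planning failure.

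**Step 1. Failures counted as non-diagnostic or dropped**

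Yield over all randomised = q × (1 − f). Yield among biopsied = q, so the biopsied-only difference is q − q = 0.

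| f_C (assumed) | Control, all randomised | New, all randomised | True gain | Biopsied-only difference |
|---|---|---|---|---|
| 5% | 0.80 × 0.95 = 76% | 80% | 4 points | 0 |
| 10% | 0.80 × 0.90 = 72% | 80% | 8 points | 0 |
| 15% | 0.80 × 0.85 = 68% | 80% | 12 points | 0 |

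With 50 in the control arm, these rates mean 2.5, 5 and 7.5 subjects, so a handful is enough.

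**Step 2. Failures in both arms**

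The true gain is q × (f_C − f_E). With f_C = 10% and f_E = 5%: 0.80 × 0.05 = 4 points (76% against 72%), again shown as 0. In this simple model equal failure rates produce no bias; the difference between arms produces it.

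**Step 3. The sign can change**

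Suppose control cannot plan a path for 20% of lesions, and the new system reaches these at a yield of only 30% (both assumed).

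- New arm: 0.80 × 0.80 + 0.20 × 0.30 = 70%.
- Control, all randomised: 0.80 × 0.80 = 64%, so the true effect is +6 points.
- Control, biopsied only: 80%, so the apparent effect is −10 points.

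A system that reaches harder lesions would look worse for doing so.

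**Step 4. If the 80% already includes planning failures**

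Then 80% is the control yield over all randomised subjects, and yield once biopsied is 0.80 / (1 − f_C): 84.2%, 88.9% and 94.1% for 5%, 10% and 15%. With the same yield once biopsied in the new arm and no failures there, the true gain is 4.2, 8.9 and 14.1 points. The biopsied-only difference is still 0. The sizes move, but the conclusion does not.

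**Step 5. What the fix does not repair**

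With 50 per arm and a two-sided 5% test (normal approximation, pooled variance under the null), power for the 4, 8 and 12 point gains in Step 1 is about 7%, 15% and 28%. A correct denominator removes the bias; it does not make the trial large enough.

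**The case against.** The strongest reply is that the sentence on biopsy sits directly after the randomisation sentence and describes a procedure, not an analysis population. Its plainest reading may be that everyone randomised was biopsied. Poor planning would then already appear as non-diagnostic biopsies, and nobody would be lost. The Background speaks of failure or inaccuracy in some areas, and an inaccurate path can still be followed and give a negative result that counts. This stands as a possible reading. It does not close the gap, because the plan nowhere adopts it and criterion (3) shows that randomised subjects can be removed.

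Several stronger readings are tempting, and the documents do not support them.

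- *That yield is taken only in biopsied subjects.* No passage says so. The text permits it and does not rule it out.
- *That planning failure is the main weakness of the old system.* It is the first of three unranked reasons, attributed to mainstream systems in general. What can be said is that it is the one the new software addresses.
- *That exclusion (1) will be used to remove subjects once the assigned plan shows no route.* The example of a hard-to-reach airway is tied to previous lung surgery, which is patient history, and it is eligible subjects who are randomised. Only an open-ended list of examples and the lack of a timing rule leave later use formally possible.
- *That the illustrated points measure bias in this trial.* The failure rates are assumed, and the 80% is an overall rate that, on the protocol's own account, probably already reflects some planning failures.

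It is also fair to say that counting these subjects as non-diagnostic is one option among several. It is the natural one here, because a system that yields no path has not delivered a diagnosis.

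**Conclusion.** The gap is real and limited. The plan does not define the denominator of its primary outcome at the step where the arms differ, and its wording allows randomised subjects with no usable path or no biopsy to be left out. Whether any such subjects exist, how many, and in which arm cannot be learned from the documents, so the bias is conditional and its direction is not fixed. Under the stated assumptions (equal 80% yield once biopsied, failures in control only at 5% to 15%), a true gain of 4 to 12 points would be reported as 0; under harsher assumptions the sign reverses. If every randomised subject was biopsied, stating the rule changes no result. This is a cheap improvement that the sponsor should make.

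**What to change.** - **Analysis set.** State in Outcomes and in the SAP that the primary analysis includes all randomised subjects in the arm assigned, and that exclusions (2) and (3) do not remove a randomised subject from it.
- **Counting rule.** State that no usable path, lesion not reached and biopsy not done each count as non-diagnostic for the assigned system.
- **Interventions.** Reword the biopsy sentence so that it says what all randomised subjects are planned to undergo, in place of what included subjects underwent. This describes the planned procedure only; the decision to biopsy an individual stays with the clinicians.
- **Exclusion (1).** State that it is settled and recorded before randomisation and is not applied after the assigned plan has been seen.
- **Reporting.** Give the number of planning failures, lesions not reached and biopsies not done by arm. Yield among biopsied subjects can be shown as a secondary figure and labelled as such.

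The document is dated within the stated recruitment period (August 2023 to December 2024). The rule should be dated and adopted before outcomes are compared by arm. For subjects already randomised, the timing of exclusion (1) can only be reported, but the denominator and the by-arm counts can still be applied.

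The cost is a few sentences, one added case report form item, and a stated yield that may be less favourable.

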To improve the diagnostic rate of lung nodules by navigational bronchoscopy, this project has conducted a preliminary exploration to address the three main issues mentioned above. The preliminary research found that the mainstream whole-lung navigation systems on the market, including The SPiN Thoracic Navigation System magnetic navigation system from Veran, the virtual bronchoscopic navigation (VBN) System from Lungpro of Broncus, and the Super Dimension Electromagnetic Navigation System from Medtronic, are all similar, although there are differences in the operation process. Despite the differences in operation procedures, the core technology of computerized virtual bronchial tree imaging is similar, and all of them are suboptimal for the reconstruction of small airways less than 3 mm. The main reason is that for small airways less than 3 mm, the airway features are not obvious or missing, which are difficult to be extracted by the existing navigation algorithms. To address this problem, on the basis of the existing algorithms to recognize airway segments, deep learning technology is added to do super-resolution reconstruction of the original CT by super-

resolution convolutional neural network (SRCNN), so as to enhance the visual features of the airway smaller than 3mm, and link the 3D-VNET network model with its own attention mechanism to intelligently recognize more small airway segments smaller than 3mm.

Study purpose and design

To improve the problems of recognition, extraction, and three-dimensional reconstruction of 2-3mm small airways that have not been solved by mainstream navigation software on the market through deep learning methods based on the VBN navigation system, and evaluate the accuracy of the improved navigation system and the original navigation system in the diagnosis of peripheral pulmonary lesions (PPL) through a randomized controlled trial.

Study population

Subjects for this single-center randomized controlled trial were recruited from August 2023 to December 2024 at the Sir Run Run Shaw Hospital, Zhejiang University School of Medicine.

Inclusion and exclusion criteria

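### The plan describes no masking of the diagnostic / non-diagnostic call, and defines no positive result, in a trial that tests the team's own system

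*Combined protocol and SAP*

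**What the plan says.** The Outcomes section gives the whole primary endpoint in one sentence: "The primary outcome was the diagnostic positive yield of the different navigation systems for PPL". It does not list the results that count as positive, say how inconclusive or non-specific findings are handled, give a time point, or name an assessor.

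On the two systems, the Interventions section says that "the small airway reconstruction system-pro (SARS-pro) (self-developed by our team) was used in the experimental group", and that a commercial virtual bronchoscopic navigation system was used for controls.

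Neither the protocol nor the SAP says whether the operator, pathologist, outcome classifier or analyst is masked. The only coding mentioned is in the ethics section, where patient identities are coded for privacy. The same section says that no commercial interests are involved. Neither statement conceals the arm from the person who judges the outcome.

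**The concern.** To compute a yield, each biopsy has to be called diagnostic or not. For clear malignancy the call leaves little room. For non-specific benign tissue, inflammation or atypical cells it is partly a judgement. Such results are to be expected here, because the inclusion criteria admit lesions that resolve poorly on anti-infective treatment as well as suspected cancers.

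Three gaps coincide: the endpoint is undefined, no masking is described, and the team is testing its own product. Randomisation does not protect against a difference between arms in how equivocal results are called. The plan as written leaves that route open for its only primary endpoint.

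**Working it through.** **Inputs**

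- Total size: "the sample size in this study was set to 100" (SAP, Statistical analysis). Allocation is 1:1 ("the old navigation system group (control group) in a 1:1 ratio"). I assume the 100 are patients, so 50 per arm.
- Yield: the Background says "the overall diagnostic rate of navigation bronchoscopy for biopsy of peripheral lung nodules is 80"%. I use this as the true yield in both arms, which is an assumption.
- Level: "Statistical significance was set to P<0.05" (SAP). Sidedness is not stated; I assume two-sided.
- Test: the SAP permits chi-square or Fisher for count data and gives no rule for choosing. I assume this covers the primary outcome and show both.
- Fraction *q* of experimental-arm negatives called positive: 20%, 30% and 50%. These are illustrative; the documents give no basis for any value.

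The plan has no figure of its own to reproduce. It states no effect size or power, so 100 cannot be derived.

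**Step 1. False-positive rate**

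With true yield *p* = 0.80 in both arms, the recorded experimental yield is *p*_E = *p* + (1 − *p*)*q*. The rejection rate is the sum, over all pairs (x, y) with P(x, y) < 0.05, of Bin(x; 50, *p*_E) × Bin(y; 50, *p*). About 50 × 0.20 = 10 biopsies per arm are truly negative, so *q* = 20% means 2 favourable calls on average.

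| *q* | Recorded experimental yield | Chi-square, two-sided | Fisher, two-sided | Chi-square, favouring new system | Fisher, favouring new system |
|---|---|---|---|---|---|
| 0 | 80% | 5.2% | 2.8% | 2.6% | 1.4% |
| 20% | 84% | 8.6% | 4.8% | 7.8% | 4.5% |
| 30% | 86% | 13.2% | 7.7% | 12.8% | 7.6% |
| 50% | 90% | 30.3% | 19.5% | 30.2% | 19.5% |

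Chi-square here is uncorrected; the Yates correction gives the same rates as Fisher. If the true yield is 70%, *q* = 20% raises the rate favouring the new system from 2.5% to 10.0% (chi-square) or from 1.5% to 6.8% (Fisher).

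**Step 2. How many calls change the conclusion**

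Take control at 40/50. Uncorrected chi-square is X² = 100(ad − bc)² / (50 × 50 × total positive × total negative).

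- 46 v 40: X² = 100 × (46×10 − 4×40)² / (2500 × 86 × 14) = 9,000,000 / 3,010,000 = 2.99, P = 0.084.
- 47 v 40: X² = 100 × (47×10 − 3×40)² / (2500 × 87 × 13) = 12,250,000 / 2,827,500 = 4.33, P = 0.037.
- Fisher: 46 v 40, P = 0.148; 47 v 40, P = 0.071; 48 v 40, P = 0.028.

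So one call crosses the threshold at 46 to 47 by chi-square and at 47 to 48 by Fisher. From an exact tie at 40 v 40 it takes 47 − 40 = 7 calls by chi-square or 48 − 40 = 8 by Fisher, out of 10 negatives. If calls are shifted in opposite directions in the two arms, it takes 4 per arm by chi-square (44 v 36, P = 0.046) or 5 per arm by Fisher (45 v 35, P = 0.023). For control counts from 35 to 42 of 50, the number needed in the experimental arm alone is 6 to 9.

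**The case against.** The strongest case against the point has four parts.

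**Silence is not evidence of an open trial.** A reader might infer that the trial is open-label and that the developers classify the biopsies. The documents say neither. The supportable statement is that no masking is described and the classifier is not named. This limits the wording of the point and leaves the gap in place.

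**A few calls would not create a result from nothing.** A reader might conclude that the trial hangs on one or two patients. That is true only when the counts already sit at the threshold, as it would be for any binary comparison; step 2 shows how many it takes from a tie. What remains is the inflated error rate, which averages over chance imbalance between the arms.

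**The size depends on the test and on assumed fractions.** By Fisher, with 20% of negatives reclassified, the two-sided rate stays below 5%. This is correct. The rate favouring the new system still rises about threefold, from 1.4% to 4.5%, but from a conservative start.

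**Defining the endpoint would remove much of the discretion.** This also stands, so the definition belongs in the fix. It does not make masking redundant, because someone must still apply the definition to borderline reports.

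**Conclusion.** The point holds in a limited form. The plan does not define a positive result and describes no masking of the pathology reading or the classification, while the team compares its own system with a commercial one. Knowledge of the arm could therefore bias the yield difference towards the new system. That direction is plausible but not certain, and the documents do not show how many results would be equivocal.

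On the stated assumptions, the effect runs from negligible or modest at *q* = 20% to a two-sided error of about 20% to 30% at *q* = 50%, depending on the test. These figures show sensitivity to biased calls and do not predict what will happen. The documents do not support saying that the trial is open-label, that the developers make the call, or that one or two patients would settle the result in general. The change is worth making because it is cheap and protects the only primary endpoint.

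**What to change.** 1. Label specimens and pathology request forms by study code, without the navigation system.
2. Before any comparison by arm, fix the list of results that count as positive, including how non-specific benign, inflammatory and atypical findings are counted.
3. Have an existing team member who neither planned nor performed that patient's procedure record the classification from the coded pathology report, before the arm is linked. The operator can hardly be masked to the navigation system, so coded forms alone would not help if the operator made the call.
4. The protocol says: "Subjects for this single-center randomized controlled trial were recruited from August 2023 to December 2024". The document is dated May 20, 2024, so some specimens may already have been read. Classify those patients from their existing reports with the arm removed. This masks the classification but cannot undo any influence on the reading itself.
5. State in the protocol who is masked and who is not.

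The cost is the work of coded labelling and a one-off reclassification of earlier reports. No extra reader, procedure or patients are needed.
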